### Incentives

To encourage participation, a teeth cleaning kit (value of HK\$ 15) will be given to participants upon completion of each survey, and another gift (value of HK\$ 25) will be given upon completion of dental examination. No incentives will be given to students to participate in the intervention activities.

## (iv) Data processing and analysis

The intra- and inter-examiner reliabilities of assessing PI, DMFT and CPI at the tooth level will be tested through the use of the kappa statistic. Data of DMFT and CPI at the tooth level will be used to generate the oral health status at the subject level.

Intention-to-treat analysis will be conducted. Multiple imputation methods will be used [40] to deal with missing data if it occurs. Between-group (intervention versus control) baseline differences in the frequency distributions of potential confounders will be compared by using chi-square test, t-test, Mann-Whitney test or other statistics. The absolute and relative risks and number needed to treat (and 95% confidence intervals) for the binary outcomes comparing the two groups at months 6 and 12 will be derived. Comparisons between the intervention and control groups will be made for all binary outcomes, adjusting for any potential confounders showing p<.10 in the between-group baseline comparisons (if any), using modified Poisson regression with robust sandwich variance estimation. SPSS will be used for data analysis; p<.05 (2-sided) will be taken as statistically significant. The research team is very experienced in performing data analysis.

Based on the number of intervention activities that the participants are actually exposed to, we will conduct a regression analysis to explore whether the incease of numbers of activities will increase the efficacy of the intervention. Subgroup analysis will also be conducted to compare the efficacy among participants who are exposed to different (or different combinations of) intervention activities.

We will consider the variables of oral health status at baseline, and test its mediating effect on the relationship between theory-based cognitions (and changes) and healthy oral behaviors (and changes). In statistics, a mediating effect can be tested by using an interaction term, whereby the effect of an independent variable on a dependent variable varies by the level of the mediator [41]. The mediating hypothesis is supported if the regression coefficient of the interaction term onto the dependent variable is statistically significant.

We will finally test a pre-designated theory-based Structural Equation Modelling (SEM) with the longitudinal data. SEM has the advantage of testing the theoretical models involving complex patterns of relationships among multiple predictors and dependent variables simultaneously [42]. As a general rule, SEM is indicated when more than one regression equation is necessary for statistical modeling of the phenomena under investigation. SEM is extremely helpful when it is truly interested in exploring a wide range of different effects and pathways (i.e., direct and indirect effects) across an entire set of variables for several different outcomes, which is exactly the current case of exploring various determinants of intention/oral behaviors/and dental outcomes.

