## Outcome indicators and potential confounders

The primary outcome is the prevalence of performing each of the three types of healthy oral health behaviors, including tooth brushing, dental flossing, and dental visit. The increase in performing healthy oral behaviors is the key of public health significance. The secondary outcome is the prevalence and severity of oral diseases, including dental caries and poor periodontal status. The third outcome is the prevalence of theory-based constructs regarding the above healthy oral behaviors, including perceived benefits, perceived barriers, perceived severity, self-efficacy and behavioural capability.

Potential confounders include socio-demographic characteristics, pre-existing oral diseases, and utilization of dental services (except for dental check-up) during the follow-up period. Such information will be collected at the baseline and follow-up survey, and between-group differences will be tested for statistical significance. Any significant differences will be adjusted in the analysis evaluating the efficacy of the intervention as compared to the control group.

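### The interaction analysis of baseline oral health status carries a support rule written for a single unadjusted test, although the analysis described implies 15 or more interactions and names no key one

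*Protocol*

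**What the plan says.** All of this is in the Protocol; no statistical analysis plan is at hand.

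- **Scope.** Section (iv) Data processing and analysis announces: "We will consider the variables of oral health status at baseline, and test its mediating effect". The relation examined is between theory-based cognitions and healthy oral behaviours, and for both the text adds changes as well as levels.
- **Verdict.** The same paragraph ends: "The mediating hypothesis is supported if the regression coefficient of the interaction term onto the dependent variable is statistically significant".
- **Threshold.** Earlier in the section: "p<.05 (2-sided) will be taken as statistically significant".
- **Constructs.** Outcome indicators and potential confounders lists five: "perceived benefits, perceived barriers, perceived severity, self-efficacy and behavioural capability".
- **Behaviours.** The same section lists three: "each of the three types of healthy oral health behaviors, including tooth brushing, dental flossing, and dental visit".
- **Status variables.** Section (iv) refers to status variables in the plural and says: "Data of DMFT and CPI at the tooth level will be used to generate the oral health status at the subject level".

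The paragraph names no primary interaction, no joint test and no rule for turning several interaction results into one conclusion.

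**The concern.** The rule speaks of one hypothesis, one interaction term and one dependent variable. The analysis it governs has several cognitions, several behaviours and more than one candidate status variable. A reader who follows the text will fit a set of interaction models and apply the 5% criterion to each, with nothing to say which result decides the matter.

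The wording is confirmatory: a hypothesis is tested and is then supported or not. In section (iv), exploratory language is attached to the regression on number of activities attended and to the structural equation model, not to this analysis.

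At stake is a secondary theoretical claim, namely that baseline oral health changes how cognitions relate to behaviour. As written, the trial could report that claim as supported on the strength of one nominally significant coefficient among many.

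**Working it through.** The Protocol gives no number of interaction tests and no family-wise error rate, so there is no stated figure to reproduce.

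**Inputs from the Protocol**
- Per-test level: α = 0.05, two-sided (section (iv)).
- Constructs: 5. Behaviours: 3 (Outcome indicators and potential confounders).
- Status variables: at least one. Two if DMFT-based caries status and CPI-based periodontal status are used separately (section (iv)).

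**Assumptions not in the Protocol**
- Each construct–behaviour pair has its own interaction test.
- No true interaction exists, and each test holds its 5% level.
- The correlation ρ between test statistics is unknown; a range is shown.

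**Step 1. Number of tests, k**
- One status variable, levels only: 5 × 3 = 15.
- Two status variables: 2 × 15 = 30.
- Change scores, or separate analyses at months 6 and 12, would raise the count further.

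**Step 2. Each pair judged separately**

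The expected number of false statements of support is k × α, whatever the correlation.
- 15 × 0.05 = 0.75
- 30 × 0.05 = 1.5

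Each single statement still carries a 5% error rate.

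**Step 3. Any one significant result counts as support**

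For independent tests, P(at least one) = 1 − (1 − α)^k.
- k = 15: 1 − 0.95^15 = 0.537
- k = 30: 1 − 0.95^30 = 0.785

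For jointly normal two-sided tests, independence gives the largest value (Šidák's inequality), so these are upper limits. With equicorrelated normal statistics, Z_j = √(1−ρ)·e_j + √ρ·u, P(max|Z_j| > 1.96) is:

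| ρ (assumed) | 15 tests | 30 tests |
|---|---|---|
| 0 | 0.54 | 0.79 |
| 0.3 | 0.46 | 0.66 |
| 0.5 | 0.36 | 0.51 |
| 0.8 | 0.20 | 0.26 |
| 0.9 | 0.14 | 0.17 |

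**Step 4. A structured check for 15 tests**

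Take the correlation between two tests as the product of the construct correlation and the behaviour correlation (1 where the construct or behaviour is shared). The chance of at least one false positive is then:
- 0.50 with correlations 0.3 (constructs) and 0.2 (behaviours)
- 0.44 with 0.5 and 0.3
- 0.34 with 0.7 and 0.5

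These correlations are also assumed.

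**Step 5. After repair**

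One pre-named joint test at 0.05 has an error rate of 0.05. Bonferroni over 15 tests would need 0.05/15 = 0.0033 per test.

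**The case against.** **The text does not say that any significant interaction suffices.** This stands. The sentence is in the singular, and a separate verdict for each pair is an equally natural reading, under which each statement carries 5%. A reader might infer that a false claim of support is about as likely as not. The document does not establish that: it needs the any-one reading, pairwise testing, weak correlation and no true interaction at all. The per-pair reading still leaves 0.75 expected false statements from 15 tests, so the rule is inadequate either way.

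**The count is inferred.** This also stands. The Protocol does not say that each construct is tested against each behaviour, and 30 tests requires two separate status scores. But the constructs, behaviours and status variables are all given in the plural, so a single test is not a plausible reading.

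**Multiplicity for an ancillary analysis belongs in the statistical analysis plan.** This would decide the matter if the Protocol were silent. It is not: it writes the decision rule and the threshold itself.

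**The related work is described as exploratory.** The text on the structural equation model and the section Purpose and potential do use such language. Neither extends it to this interaction analysis.

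**The consequences are small.** Largely right. The analysis appears in neither the Objectives nor the Hypotheses. A reader might infer that a spurious interaction could drive scale-up or redirect the programme. Purpose and potential ties scale-up to the intervention being effective, and the interaction is between cognition and baseline status, not between arm and status.

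**The clearer fault is calling an interaction a mediating effect.** A significant interaction indicates effect modification, and correcting the count does not cure that. Equally, renaming the effect leaves the same set of unadjusted tests under the same rule.

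**Conclusion.** The point holds in a limited form. The Protocol fixes a confirmatory criterion that suits one test and applies it to an analysis that implies at least 15 interactions if they are tested pairwise, with no key interaction and no way to combine results.

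Its size depends on the reading. Judged pair by pair, an average of 0.75 false statements of support is expected from 15 null tests. If any one result counted, the chance of at least one is bounded by about 54% and falls to about 36% or 20% at assumed correlations of 0.5 or 0.8. These figures assume that no true interaction exists, and the correlations are not in the Protocol.

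The effect is confined to a secondary theory claim. The comparison of intervention with control is untouched.

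**What to change.** Replace the last sentence of the paragraph in section (iv) with:

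> These interaction (effect-modification) analyses are exploratory; all interactions tested will be reported with 95% confidence intervals and no hypothesis will be declared supported from a single significant interaction.

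The preceding sentences, which call the effect mediating, should be brought into line with this.

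If a confirmatory statement is wanted, pre-name one joint Wald test of the five construct-by-status interactions for tooth brushing, with one named baseline status variable, at two-sided 0.05. The other interactions stay exploratory.

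The cost is wording only: no change to data collection, sample size or design. The downside is that a single nominally significant interaction can no longer be presented as support.

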# (v) Purpose and potential

This is the first peer-lead theory-based RCT tested in adolescents in HK. The intervention activities cover 3984 S2 students in secondary schools, and the improved cognitions and healthy oral behaviors will benefit adolescent's oral health substantially from adolescence to adulthood. The longitudinal data make path analysis possible to explore the existence and strength of both direct and indirect (mediating) effects. It provides evidence to health care providers on decision making regarding cost-effectiveness.

If this intervention is found to be effective, the peer-lead theory-based intervention can be scaled up to the rest secondary schools. All developed education materials can be reused. At the same time, the well-trained peer leaders are also able to deliver intervention activities after the funding period to keep a sustainable effect. These peer leaders also have the capacity to deliver other peer-led activities (e.g., physical activity, depression prevention), which will contribute further to the building of adolescents' general health.

Last but not least, in addition to the improvement of adolescent's oral health related cognition and skills, the community (secondary schools) have been actively involved and empowered, which is beneficial for community health outcomes of Hong Kong in the long run.

